created for this project, on the same schedule as peer mentoring sessions. Both conditions will be delivered via Webex, which has several advantages for this intervention: 1) Sessions are easily accessible via phone or computer, allowing participants to choose their preferred interaction style; 2) A study coordinator can host the support groups and drop in/out for monitoring purposes; 3) There are video- or voice-call options for up to 25 participants at a time; and 4) This application ensures concordant delivery methods across both arms of the study and the ability to document the frequency that voice and video options are used to adjust for participant choices in analyses. All participants (mentees, mentors, and social support controls) will be assessed using validated measures of patient reported outcomes and clinical indicators of disease activity at baseline, mid-intervention (3 months from baseline), immediately post-intervention (6 months from baseline), and 6 months post-intervention (12 months from baseline). For each wave, outcomes for mentees randomized to the mentored group will be compared with the outcomes of mentees randomized to the support group. A booster session will be incorporated for all participants (mentored and support group) at 3 months post-intervention to encourage retention.[102]

B4c. Scientific Rigor: Assuming 3 post-randomization measurement time points, level of significance p=0.05, two-tailed comparison, correlation between pairs of measurements within participants (interclass correlation) no larger than p=0.7, AR(1) covariance structure, we estimate that 123 participants per group (total n=246) are needed to detect, with 80% power, a standardized effect size of 0.35sd with 20% inflation for attrition at 12 months. This study will apply strict principles of randomized clinical trials including randomization, blinding, careful tracking of all participants and intent-to-treat analyses to ensure robust and unbiased results.

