**Data Collection Strategy** 

Data Collection Process/Schedule: Fourteen trained peer mentors will deliver the intervention in each wave and one full-time study coordinator (SC) will conduct screening, consent, enrollment procedures, and support group moderation. The primary method of data collection will be face to face interview. Mentees will be assessed at baseline, mid-intervention (3 months from baseline), immediately post-intervention (6 months from baseline), and 6 months post-intervention (12 months from baseline). Physical examination and laboratory evaluation will be achieved by in-person clinic visit when recent SLEDAI scores are not available in the database record of a given participant. Social support control participants will complete assessments on the same schedule as mentored participants. Given evidence that peer support may be just as beneficial to the supporters as it is to the person being supported, [118,119] mentors will be assessed on the same schedule as mentored and control participants, using the same tools.

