Disease activity will be assessed using both physician assessment and patient-reported outcome measure. The Systemic Lupus Activity Questionnaire (SLAQ)[131] asks a single Patient Global Assessment (PGA) question about presence and severity of lupus activity over the past month, questions on 24 specific symptoms of disease activity and a single Numerical Rating Scale (NRS) asking the patient to rate disease activity on a scale of 0-10 over the past three months. Use of immunomodulatory drugs and prednisone (total dose and tapers) will also be assessed. For physician assessment of disease activity, the Systemic Lupus Erythematosus Disease Activity Index (SLEDAI) has been individually validated and found reliable in clinical trials. SLEDAI scores are routinely collected as part of regular visits and clinical, demographic, genetic, disease activity/damage, genetic, and laboratory data are stored in the longitudinal web-based SLE database at MUSC as part of NIH-funded P60 and P30 grants (see [name] biosketch). All clinicians recording SLEDAI scores are trained in this assessment with annual refresher courses as part of their participation in industry-sponsored clinical trials. SLEDAI scores for each participant will be extracted from the database when available for dates within the same month as baseline, mid-intervention, and post-intervention data collection points. When scores are not available in the database, the participant will be scheduled for a clinic visit that will include vitals, blood collection, and labs to ascertain SLEDAI score. Clinic visits will take place within the South Carolina Clinical & Translational Research Institute (SCTR) Research Center (Research Nexus) at MUSC. The SC will coordinate questionnaire administration, clinic visits for SLEDAI ascertainment, and data entry. Physical examination and laboratory evaluation will be achieved by in-person clinic visit when recent SLEDAI scores are not available in the database record of a given participant. Social support control participants and mentors will complete assessments on the same schedule as mentored participants. The SLEDAI is a multicomponent, 24 question survey of clinical and laboratory signs and symptosm used as a representation of a physician's assessment of a patient's disease activity over the last 30 days (see Appendix). Items are weighted based on their severity ranging from a multiplier of 8 to no multiplier (i.e. 1). The maximum 'score' for the test is 105.[132] Validated clinically meaningful changes in SLEDAI scores are -6 for improvements and +8 for worsening disease activity.[133]

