Missing data: We will handle missing data using several techniques including multiple imputation and maximum likelihood,[149] and latent class based multiple imputation.[150] Missing data mechanisms will be examined using both univariate and multivariate methods. We will check for missing at random (MAR) by creating a missing indicator for each missing variable and study the predictors of missingness using logistic regression. If any of the fully observed covariates or outcomes become significant in the missing data model then we will use methods for MAR if we do not have any reason to believe that the missing data mechanism is not at random.

Mid-point Analyses for the protection of participants: In an effort to protect both mentors and mentees from potential deleterious effects of mentoring, a mid-point (interim) analysis will be undertaken to assess safety using 3-month post-intervention data. If mentored participants have worsened beyond a threshold, we will stop the trial for ethical concerns. For instance, if the lower confidence limits based on 95% confidence interval at the midpoint, for any one of the variables, namely depression, anxiety, and/or disease activity, is larger than 50% compared with their baseline measure, the trial will be terminated. Similarly, mentors will be monitored for depression, anxiety, and disease activity and if a worsening trajectory is observed at mid-point analyses, they will be removed from the study.

AIM 3: Determine the cost and cost-effectiveness of a peer mentorship intervention on disease self-management, disease activity, and HRQOL, in African American women with SLE.

The cost of the intervention will be compared to the outcomes of the intervention 12 months post baseline. In order to compare with previous lupus studies,[151,152] Quality adjusted life years (QALYS) will be calculated for intervention and control groups based on the SF36 outcome which will be measured 12 months post baseline. The calculation will be based on an established peer reviewed method.[153] Measuring QALYS gained relative to cost of the intervention is the preferred outcome method for the American College of Physicians (ACP).[154]

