- B. Data Collection Schedule: At the baseline visit, the RC will give detailed explanation of the study, the reimbursement schedule, and obtain consent. Participants will provide a blood sample, if necessary, and complete a questionnaire that captures demographics, health literacy, coping, disease activity, disease self-management, anxiety, depression, perceived stress, social support, trust, patient centered care, perceived control, perceived discrimination, spirituality, and quality of life. The RC will review study goals, establish the schedule of study sessions, obtain contact information (primary and alternate telephone numbers), and receive study materials. After the baseline assessment, follow-up assessments will be conducted at 6 months (questionnaire only) and 12 months (questionnaire and blood collection). As much as possible, research visits will be scheduled on the same day as their clinic visit. Mentors and mentees will be on the same schedule of data collection, regardless of whether a mentor has assigned mentees after their enrollment.

Potential risks to mentees and mentors include: 1) discomfort, bruising, or scarring from venipuncture, 2) possible violation of the patient's privacy, 3) discomfort with questions on the research questionnaire, and 4) psychological distress. Additional risks to mentors specifically include: 1) discomfort with interactions with mentees and 2) feeling overwhelmed. Details on how these risks will be minimized are discussed under adequacy of protection against risks below.

Confidentiality: This will be maintained by keeping participant folders in locked file cabinets in the research center. Only participants' unique identification numbers will be recorded in folders and on data forms. The database will remain on the MUSC computer system that use unique ID numbers, rather than names, and will be password-protected. To further ensure confidentiality, participants will be provided

with a basic phone and calling/texting plan for the duration of the study for mentoring interactions so that personal phones are not used.

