- 1. Upon enrollment, peer mentors will receive training, prior to working with mentees.
- 2. Mentors will be given a written manual presenting all the material in detail for their ongoing reference.
- 3. Mentors will be given parameters for their roles and instructed on how to handle potential issues that may arise (e.g. not providing clinical advice) along with role-playing.
- 4. After the initial training, peer mentors will continue to meet with the PI weekly to identify challenges and reinforce the guidelines for peer mentors. During these meetings, the PI will also monitor mentors' comfort with interactions and their mentee load. If mentors express discomfort and/or feeling overwhelmed, mentees will be reassigned and/or redistributed.
- 5. Bi-weekly surveys to mentees and PI meetings with mentors will be used to track participant satisfaction with the peer mentoring process.

Additional protections against potential risks include the following:

- 1. Psychological Distress: Because we will be administering a questionnaire that measures the presence of depression, we will take several steps to ensure the safety of research participants. RAs will be trained by the PI to identify patients who meet criteria for depression on the PHQ-9. Participants who screen positive for depression will be assessed by a clinician before leaving their study visit to ensure their well-being and verbally instructed to seek care from their PCP. If deemed appropriate, they will also be given the Suicide Prevention National Hotline, [name], and told to call if they experience acute worsening of symptoms before they can be seen by their PCP.
- 2. Administration of Research Questionnaires: Some participants might be offended by detailed questions about emotional or physical health status and impairment. All participants will be informed at the outset that they may terminate participation at any point. Past research suggests that data collection using these measures can be conducted without undue psychological distress or exacerbation of symptoms among study participants.
- 3. Unknown risks: Participation in research may have other unknown risks. The researchers will advise participants if they learn of emerging information that might alter participants' decisions to participate.

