On a daily basis, the PI and Biostatistician will ensure the security of all data files. At critical data collection junctures (baseline, mid-intervention, immediately post-intervention and 6 months postintervention), the PI will review the data set to ensure de-identification prior to analysis. It is the Biostatistician's responsibility to enter, manage and analyze data, and transmit outputs and summarized results to the PI, as appropriate. On a bi-weekly basis (according to the schedule of intervention and support group sessions), the PI will monitor mentor and mentee reports of their activities and communications to ensure that they are safe and to detect any unexpected adverse events and report any concerns to the institutional IRB. Summaries of adverse events reports or patient safety concerns reported to the IRB will be made to NINR in the annual progress report unless the nature of a particular event is such that it warrants immediate reporting. If any adverse events or serious adverse events occur during the conduct of this study, they will be reported to the MUSC IRB in accordance with Section 4.7 -Unanticipated Problems and Adverse Events Policy and Procedures. The timeframe for collecting adverse events will be from the time of enrollment to last follow-up. Adverse events will be collected during each follow-up phone call or meeting by prompting participants to let the study coordinator or other research team member know if they have experienced any adverse events. In addition, should events be reported in-between follow-up calls, those will be recorded immediately. The study coordinator will inform the principal investigator of SAE and AEs by phone or secure email communication. The principal investigator will, in turn, inform the IRB immediately by updating the study record in the Health Sciences South Carolina (HSSC) eIRB system. As the PI receives notification of any study-associated adverse event, that information will be immediately shared with the overseeing IRB. Notification of an adverse or serious adverse event may be provided by the participant, MUSC study coordinator, etc. All Serious Adverse Events (SAE's) will be reported to NINR within 48 hours of the Principal Investigator becoming aware of the event.

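### Mentors who worsen at the mid-point are removed from the study, and no follow-up is scheduled to see whether the worsening resolves

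*Combined protocol and SAP*

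**What the plan says.** The paragraph on mid-point analyses for the protection of participants, in the Overview of Statistical Analysis Plan, sets up an interim safety look. For mentors the consequence of worsening in depression, anxiety or disease activity is that "if a worsening trajectory is observed at mid-point analyses, they will be removed from the study". The same sentence appears in the human-subjects text after the steps for negative mentor–mentee interactions, and again in the safety-monitoring text after adverse event reporting.

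Mentors are otherwise followed in full. Data Collection Process/Schedule states that "mentors will be assessed on the same schedule as mentored and control participants, using the same tools". Section B4b sets the post-baseline times as "mid-intervention (3 months from baseline), immediately post-intervention (6 months from baseline), and 6 months post-intervention (12 months from baseline". On adverse events, the safety-monitoring text says: "Adverse events will be collected during each follow-up phone call or meeting by prompting participants". The window for this runs from enrollment to last follow-up.

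A mentor's exploratory outcome data are analysed with the same methods as the mentees' (exploratory analyses paragraph), without power for that purpose.

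**The concern.** The rule exists to protect mentors from possible harm caused by mentoring, but it takes them out of the study and not only out of the mentoring role. The mentors whose scores have moved the wrong way are the ones whose later scores matter most for safety. If they leave all assessments, the study has no planned means of learning whether the worsening persists, resolves after mentoring stops, or progresses.

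Two things are at stake: safety follow-up of enrolled participants who themselves have SLE, and the completeness of the exploratory analysis of how mentoring affects mentors.

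**Working it through.** No formula applies. The check sets the relevant provisions side by side and then counts what is left after removal.

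**Does removal mean leaving the study?** The protocol separates a change of role from leaving the study. In the list of protections, item 4 says: "If mentors express discomfort and/or feeling overwhelmed, mentees will be reassigned and/or redistributed". In the steps for negative interactions, an unresolved pairing leads to reassignment, while persistent breaches may lead to a participant being asked to leave the study. The mid-point rule uses the language of leaving the study, so that is the plain reading. No section states outright that follow-up stops.

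**Does any other provision schedule follow-up after removal?**

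| Provision | What it covers | Does it fill the gap? |
|---|---|---|
| Data Collection Schedule: "Mentors and mentees will be on the same schedule of data collection, regardless of whether a mentor has assigned mentees after their enrollment" | Mentors who have no mentees | No; it does not mention mentors removed for worsening |
| Protections, item 4 | Mentors who express discomfort or overload | No; it is triggered by what she says, not by her scores |
| Psychological Distress item: "Participants who screen positive for depression will be assessed by a clinician before leaving their study visit" | Clinician check, primary-care advice and, if appropriate, a crisis line | Directs her to care at that visit; no reassessment is set |
| Referral text in the human-subjects section | Referral of serious problems; medical guidance for study-related events | Care, not planned observation of outcome |
| Adverse event collection | Prompted at follow-up contacts; events reported between calls are also recorded | Prompting ends with the contacts |
| Methods for Aim 2: "SLEDAI scores are routinely collected as part of regular visits" | Disease activity at routine visits | Partly; extraction is tied to study time points, and mentors may be recruited from outside the database |

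Of the three monitored measures, only disease activity (through SLEDAI) has a stated routine source. Depression and anxiety, 2 of 3, have none.

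**What is lost?** Inputs: post-baseline assessments at months 3, 6 and 12 (B4b), with last follow-up taken as month 12 for one cycle. The mid-point paragraph speaks of data three months post-intervention, which can be read in two ways.

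- *Month 3 from baseline.* This is the scheduled mid-intervention assessment. Lost: months 6 and 12, which is 2 of 3 post-baseline assessments. Prompted adverse event collection lost: 12 − 3 = 9 months.
- *Three months after the intervention ends.* The intervention ends at about month 6, so this is 6 + 3 = about month 9. A booster session falls there, but no assessment does. Lost: month 12, which is 1 of 3. Prompted adverse event collection lost: 12 − 9 = about 3 months.

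Month 3 fits the schedule better. On either reading, no scheduled assessment remains after removal.

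**Limits of the count.** The Data Collection Schedule item lists follow-up only at months 6 and 12. On that list the month 3 reading still loses both, but the denominator is 2. Recruitment of Mentors intends mentors to serve several groups, so more than one cycle could be lost. The plan does not say whether the mid-point look is made once for the trial or once per wave; if once, time at removal depends on the mentor's wave.

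**The case against.** The strongest reply is that this is a matter of wording. No sentence says that assessments cease, mentors without mentees stay on the data schedule, and a mentor found to be depressed is seen by a clinician, told to consult her primary-care physician, and can be referred. Mentors are not randomized, and their analysis is exploratory and unpowered.

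Much of this stands. A reader might infer that a removed mentor is left without care; the provisions for clinician check, referral and medical guidance contradict that. A reader might also infer that removal biases the trial's results. The documents do not support that either: the randomized comparison is between mentees, and within the mentor data the planned likelihood and imputation methods under missing at random can handle removal that depends on recorded scores. Nor can one say how many mentors would be affected. About 30 are expected and at most 60, but what counts as a worsening trajectory is not defined.

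What does not stand is that the gap is only an omitted detail. The rule is stated, and following it as written ends scheduled observation. Care at the visit where worsening is found does not show what happens afterwards.

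**Conclusion.** The point holds as a gap in safety follow-up. On the plain reading of the rule, the study would not systematically observe whether a removed mentor's worsening resolves. The loss per removed mentor runs from one assessment and about 3 months of prompted adverse event collection (mid-point near month 9) to two assessments and about 9 months (mid-point at month 3). These figures assume one 12-month cycle and that removal from the study ends study contacts. The total loss across mentors cannot be estimated. The consequence is confined to mentor safety and the exploratory mentor analysis. It is a cheap improvement.

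**What to change.** In all three places where the rule appears, replace the clause on removal with: *they will be released from mentoring and their mentees reassigned, while remaining in all scheduled assessments and adverse event collection to month 12 unless they choose to withdraw.*

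Keep the release mandatory; making it discretionary would weaken the protection. Reassignment of mentees is already a study procedure. The exploratory analysis paragraph needs no change, since it excludes no mentor and its methods use all available scores.

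The cost is one clause, repeated three times. The downside is that released mentors continue to complete questionnaires, and attend a SLEDAI visit when no score is in the database. All of this is already on their schedule.

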
study, the most valued aspect of the program was interaction with their peers, which informs the proposed intervention.

4. The Peer Approaches to Lupus Self-Management (PALS) Pilot Study. The PALS intervention was piloted with African American women with lupus enrolled in the SLE database at MUSC. Seven mentors were trained and paired with 21 mentees to provide modeling and reinforcement to participants by telephone for at least 60 minutes every week for 12 weeks. Mentee outcomes of self-management, disease progression (including disease activity, damage, and cytokine balance) were obtained at baseline, mid-intervention (6 weeks from baseline), and immediately postintervention (12 weeks from baseline), using validated tools. Qualitative data were also collected over the course of the study in the form of weekly mentee check-ins, mentor logs, and an end-of study focus group. While the PALS pilot lacked a control group, it provided a sense of general effect size and was used to design the current study.[107,108] At post-intervention, we observed statistically significant decreases in patient-reported disease activity (significant change score of 24,70 or 25% change in patient global assessment of overall lupus disease activity, p<0.001). incrementally improving trends in patient activation, and statistically significant decreases in depression (significant change score of 2.62 or 11% change in PHQ-8 score, p=0.05) and anxiety (significant change score of 3.52 or 15% change in GAD-8 score, p=0.018). Student t tests were also conducted to compare 2-month pre- and 2-month post-intervention hospitalization charges. Mean charges per person were \$24289 prior to intervention and \$872 post intervention, providing very strong evidence for the intervention's potential to reduce inpatient charges post intervention.[109] In addition, both mentees and mentors gave very high scores for perceived treatment credibility and service delivery, providing preliminary support for the efficacy, acceptability, and perceived credibility of the PALS intervention.[87,88,97] In summary, our preliminary studies demonstrate that in African American women with SLE, selfmanagement education delivered in weekly sessions led to improvements in lupus self-efficacy, health distress, and depression, and that more culturally targeted information and increased social support could yield more significant improvements in quality of life. More importantly, results of BLESS and IQAN studies, feedback from patients, extensive review of the literature and preliminary data from the PALS pilot study suggest that a peer mentoring intervention is credible, acceptable and likely to be effective at improving self-management, decreasing disease activity and improving quality of life in African American women with SLE. Additionally, using the same outcome measures across investigations will allow comparison of the impact of the current culturally tailored approach to the untailored "Better Choices, Better Health" intervention used in the BLESS study with this patient population.

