Using QALYs, the incremental cost-effectiveness ratio (ICR) can be calculated as: (QALYintervention-QALYcontrol)/(Costintervention-CostControl). The ICR can then be compared with the ICRs for previous lupus interventions. We will take the perspective of the provider, insurer and patient. All three are affected in the hospitalization charges since insurers pay part and patients will pay part of the charges. In addition to the main cost-effectiveness outcome of QALY and the ICR, costs of the

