intervention can be compared with any changes in MUSC health services utilization costs for emergency department, inpatient and outpatient care for the intervention relative to the control group. In addition to a comparison of intervention cost with average difference between MUSC costs for intervention and control group 12 months post baseline, generalized linear cost models can be estimated to examine the association of the treatment with MUSC health services costs while adjusting for patient demographics (age, gender, race/ethnicity, co-morbidities) and clinical outcomes. MUSC does not provide cost information, only charges. In addition we will estimate the impact on work loss and income by estimating the changes in days lost to illness and income based on values provided by participants. We will use the year for which the hospital charge and income data is reported and adjust for inflation as appropriate using the US Department of Labor Consumer Price Index. Inpatient and outpatient MUSC costs will be compared separately and together between the control and intervention groups. Bootstrapping methods will be used to conduct sensitivity analyses for all cost models. Sensitivity analysis will be performed by estimating a separate MUSC health services cost model while adjusting for each clinical outcome to insure robust results regarding the marginal effect of the treatment on MUSC health services costs. Park tests will be conducted to determine the best fit for the cost data in specifying the generalized linear model. In the event of many zero values, a two-part model will be used to first examine the association of the treatment with the likelihood of any MUSC costs and then the conditional generalized linear cost model, conditional on having non zero MUSC cost value for the patient. The ICR will be reported as a single ratio with no uncertainty attached to it. Therefore, standard statistical characteristics such as confidence intervals or hypothesis test to compare it to an a priori ICR from another study are not applicable. We will calculate the ICR and a clinically relevant interpretation of the outcome will be p Human Subjects Involvement and Characteristics. The Peer Approaches to Lupus Self-Management (PALS) study is a randomized controlled trial designed to examine whether a new, culturally tailored peer mentoring intervention improves disease self-management, indicators of disease activity, and health related quality of life (HRQOL) in African American women with systemic lupus ervthematosus (SLE). African American women with active SLE will be recruited as mentees and peer mentors who are considered competent in the management of their condition will be identified and recruited to provide modeling and reinforcement to participants. We will recruit mentees for 300 observations (150 mentored and 150 support group) and up to 60 mentors. Mentees and mentors will be primarily recruited from the longitudinal web-based SLE database at the Medical University of South Carolina (MUSC) in three cohorts. As part of each cohort, mentors (n=20) will be trained to deliver intervention content, prior to being paired with up to three mentees (n=50). The peer mentoring intervention will occur by twelve 60minute telephone or video sessions carried out across the course of 24 weeks. In each cohort, social support controls (n=50) will participate in a lupus support group created for this project, on the same schedule as peer mentoring sessions. All participants (mentees, mentors, and social support controls) will be assessed using validated measures of patient reported outcomes and biological indicators of disease activity at baseline, mid-intervention (3 months from baseline), immediately post-intervention (6 months from baseline), and 6 months post-intervention (12 months from baseline). For each cohort, outcomes for mentees randomized to the mentored group will be compared with the outcomes of mentees randomized to the social support control group. A booster session will be incorporated for mentored participants at 3 months post-intervention to encourage retention.

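### Aim 3 defines the incremental cost-effectiveness ratio as QALYs over cost, the reciprocal of the conventional ratio, so comparing it with cost-per-QALY figures from earlier lupus studies would be invalid

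*Combined protocol and SAP*

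**What the plan says.** The AIM 3 text in the Overview of Statistical Analysis Plan names the measure and gives its formula: "the incremental cost-effectiveness ratio (ICR) can be calculated as: (QALYintervention-QALYcontrol)/(Costintervention-CostControl". The stated use follows at once: "The ICR can then be compared with the ICRs for previous lupus interventions". Comparison with earlier work is also the reason given for choosing QALYs ("In order to compare with previous lupus studies"). A sentence just before the formula describes the measure in the same orientation: "Measuring QALYS gained relative to cost of the intervention is the preferred outcome method". QALYs and this ratio are named together as the main cost-effectiveness outcome.

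Later in the same section the plan states: "The ICR will be reported as a single ratio with no uncertainty attached to it". Bootstrapping is planned, but only for the cost models: "Bootstrapping methods will be used to conduct sensitivity analyses for all cost models". The plan gives no unit for the ratio, does not say whether higher or lower is better, sets no threshold, and has no rule for a negative value or a denominator near zero. It does not state the unit or orientation of the earlier ratios.

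**The concern.** An incremental cost-effectiveness ratio is conventionally the extra cost divided by the extra effect, in dollars per QALY gained, with lower being better when both differences are positive. The plan uses that name for the reciprocal, which has a different unit and the opposite direction of benefit.

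This would be only a matter of labelling if the ratio stayed inside the trial. Its stated use, however, is comparison with published ratios, and it is to be reported as one number with no uncertainty. A reader who sets it beside cost-per-QALY figures compares quantities on reciprocal scales. A reader who applies the usual lower-is-better rule to it would prefer the worse programme. Because the nearby wording leans the same way as the formula, an analyst cannot safely treat the formula as a typing slip and correct it silently.

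**Working it through.** The documents give no value for the ratio, the QALY difference (dQ), the cost difference (dC) or a threshold, so there is no figure to reproduce. All values of dQ, dC, standard deviation and benchmark below are assumptions for illustration. From the documents come the formula, the 123 participants per group (Power and Sample Size Justification) and the pilot charges (Feasibility & Preliminary Data Relevant to the Proposed Work, item 4).

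**1. Unit and direction.** As written, the ratio is dQ/dC, in QALYs per dollar. The conventional ratio is dC/dQ, in dollars per QALY. Each is 1 divided by the other. With dQ = 0.02:

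| dC | dQ/dC (as written) | dC/dQ (conventional) |
|---|---|---|
| $500 | 0.02/500 = 0.00004 | 500/0.02 = $25,000 |
| $2,000 | 0.02/2,000 = 0.00001 | 2,000/0.02 = $100,000 |

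The better programme has the larger number as written and the smaller number conventionally.

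**2. What the comparison does.** Take dQ of 0.01, 0.02 and 0.05 with dC of $500, $1,000 and $2,000, against an assumed benchmark of $50,000 per QALY. The nine conventional ratios run from 500/0.05 = $10,000 to 2,000/0.01 = $200,000: four below the benchmark, two equal to it and three above.

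- Raw comparison: the written ratio runs from 0.000005 to 0.0001, so all nine cases fall below 50,000. That is right for four and wrong for the three above the benchmark. The comparison carries no information.
- Benchmark turned over to 1/50,000 = 0.00002 and higher read as better: the same four cases pass. The conclusion matches the conventional one.
- Benchmark turned over but lower still read as better: exactly the three worst cases pass. Only this reading reverses the result.

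**3. Denominator near zero.** As written, with dQ = 0.02: dC = $1,000 gives 0.00002, dC = $1 gives 0.02, and dC = -$1 gives -0.02. In the conventional form, with dC = $1,000: dQ = 0.02 gives $50,000, dQ = 0.0002 gives $5,000,000, and dQ = -0.0002 gives -$5,000,000. Turning the ratio over moves the problem from the cost difference to the QALY difference.

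**4. How often each denominator could change sign.** Assume a true dQ of 0.02, a true dC of $500, a QALY standard deviation of 0.10 to 0.20 and a cost standard deviation of $10,000 to $30,000, with normal estimates and 123 per group. The standard error is the standard deviation times the square root of 2/123.

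- Cost: $1,275 to $3,825, so the estimated dC is negative in about 35% to 45% of trials.
- QALY: 0.0128 to 0.0255, so the estimated dQ is negative in about 6% to 22%.

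In simulation under these assumptions, the central 95% range spans zero for both ratios.

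**5. Sign.** The pair (dQ = +0.02, dC = -$1,000), better and cheaper, and the pair (dQ = -0.02, dC = +$1,000), worse and dearer, both give -0.00002 as written and -$50,000 conventionally. A negative ratio cannot tell them apart in either form.

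**The case against.** The strongest defence is that the formula and the sentence before it agree. Read as QALYs bought per dollar, with higher better and with benchmarks put on the same scale, the written ratio ranks programmes just as the conventional one does when both differences are positive. A raw comparison of 0.00002 with 50,000 is also so plainly a mismatch of units that an analyst would probably notice it. Both points stand. They limit the harm but do not make the formula match the measure it names or the stated comparison.

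Three stronger inferences are tempting, and the documents do not support them.

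- A reader might infer that the plan would reverse the conclusion on cost-effectiveness. That requires the inverted figure to be read as lower-is-better, and the plan nowhere says so.
- A reader might infer that Hypothesis 3 stands or falls on this ratio. The hypothesis is worded in terms of QALYs, no threshold or decision rule is tied to the ratio, and the plan says a test against another study's ratio does not apply.
- A reader might infer that the inversion causes the instability and that the pilot shows a cost difference near zero. Working steps 3 and 5 show that the conventional form has its own divergence and the same ambiguity of sign. The pilot reports "Mean charges per person were \$24289 prior to intervention and \$872 post intervention", a fall of 24,289 - 872 = $23,417. This is an uncontrolled change in hospitalization charges between two-month periods. It shows that a negative cost difference is conceivable and no more, and a difference of that size would not be near zero.

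It is also fair to say that part of the remedy is already planned: QALYs are calculated for each group, and health-service costs are compared between groups.

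**Conclusion.** The formula is wrong for the measure it names. It is the reciprocal of the conventional ratio, and nothing elsewhere in the documents corrects it. If the earlier lupus ratios are cost per QALY, the planned comparison is invalid as written and can mislead, as the inverted order of 0.00004 and 0.00001 against $25,000 and $100,000 shows. That condition is the usual convention but remains an assumption. The supportable conclusion is an invalid comparison, not a reversed finding.

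Instability belongs to ratios of this kind in either orientation and is not an effect of the inversion alone. The frequencies of sign change rest wholly on assumed means and standard deviations. Reporting the ratio without uncertainty is a separate matter that the inversion neither causes nor cures.

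The error is confined to Aim 3. The conventional ratio can be calculated from the same two differences, so no data are lost if the text is corrected before the Aim 3 analysis.

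**What to change.** In the AIM 3 text of the Overview of Statistical Analysis Plan:

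1. Replace the formula with (Cost intervention - Cost control)/(QALY intervention - QALY control), in dollars per QALY gained, and state that lower is better when both differences are positive.
2. Report the incremental cost and the incremental QALYs beside the ratio in every case, so that a near-zero QALY difference is visible.
3. Where the differences have opposite signs, state in words which arm is less costly and more effective, in place of a negative ratio.
4. Before comparing with earlier lupus interventions, confirm that each published ratio is in cost per QALY.

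Reword the sentence on QALYs relative to cost to match. The change costs one formula and a few reporting sentences. It needs no new data, does not alter Aims 1 and 2 or the sample size, and has no evident downside.
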